## Protocol summary

Optimizing enteral nutrition (EN) is challenging in extremely preterm infants due to feeding intolerance that relates to the functional gastrointestinal immaturity. Early feeding is a safe way to promote postnatal gastrointestinal maturation and, when compared with delayed enteral feeding, provide benefit, such as reduced time to full enteral feedings (TFF) and number of parenteral nutrition (PN) days. Failure to develop oral feeding competence often leads to growth failure, longer hospital stays, dependence on PN and its complications, and influences long-term growth and developmental outcomes. Feeding with human breast milk has a protective effect against necrotizing enterocolitis (NEC) compared with formula, whereas feeding intolerance is one of the early signs of NEC. Delayed passage of meconium is a risk factor for feeding intolerance in preterm VLBW neonates and specific meconium microbiota characteristics have been linked to increased risk of NEC. This randomized controlled trial (RCT) aims at evaluating the effect of regular intestinal lavage using normal saline on the TFF and severe complications such as NEC and sepsis, in extremely preterm infants. We aim also to follow children's neurological development until 5,5 years of age. The study will include one intervention group of 100 subjects that will receive regular rectal washout with normal saline and equal number of control subjects, treated according to current routine. The trial is preliminarily estimated to last between year 2018 and 2022. Investigators will monitor closely for possible adverse events. The results are going to be published in reviewed medical journal.

## Background

Optimizing EN is challenging in preterm very low birth weight (VLBW) neonates, due to feeding intolerance that relates to the functional immaturity of their gastrointestinal (1,2), neurologic, cardio-respiratory, and oral-motor systems (1). The introduction of enteral feeds for extremely preterm or VLBW infants is often delayed for several days or longer after birth due to concern that early introduction may not be tolerated and may increase the risk of NEC, a devastating intestinal disease. However, a recent Cochrane meta-analysis indicated that delayed introduction of progressive enteral feeds do not reduce the risk of developing NEC in very preterm or VLBW infants (3). Moreover, strong evidence suggests that early feedings are a safe way to promote postnatal gastrointestinal maturation, and when compared with delayed enteral feeding, provide benefit to this vulnerable population, such as reduced TFF and number of parenteral nutrition (PN) days (4).

Failure to develop oral feeding competence often leads to poor nutritional status, growth failure, longer hospital stays, increased costs of care, and influences long-term growth and neurodevelopmental outcomes (2). Feed intolerance is associated with delayed maturation of gut function as well as prolonged TFF and dependence on PN (1,5,6). PN provides life-saving artificial nutrition and adequate growth in infants with insufficient intestinal function due to prematurity and/or major abdominal gastrointestinal surgical procedures but is also linked to severe complications. More specifically, PN is associated with increased rates of bacterial and fungal sepsis due to the requirement for central line for infusion, and intestinal bacterial overgrowth caused by enteral starvation and immature immune function (1,7,8). Moreover, the use of PN increases the risk of mechanical complications related to venous line placement as well as miscalculations and errors in PN manufacture, supply and administration (7). Intestinal failure-associated liver disease (IFALD) is a potentially life-threatening problem in patients receiving long-term PN, and preventive strategies include early enteral feeding, weaning of PN, reduced dose lipid emulsions and early recognition and treatment of sepsis (5–8). Inadequate breastfeeding and severe weight loss are known risk factors for

unconjugated hyperbilirubinemia in term and late preterm babies; however, there is paucity of data about the effect of enteral feeding on the risk of jaundice in extremely preterm infants (9).

NEC is a multifactorial disease primarily affecting extremely preterm and VLBW infants, leading to profound inflammation and intestinal injury with severe morbidity and mortality if not identified and treated early (10). Clinical signs and symptoms are nonspecific and include temperature instability, bradycardia and apnoea, hypotension, abdominal wall erythema, increased pre-gavage residuals, abdominal distention, emesis, blood in the stool, absent bowel sounds, abdominal tenderness, and occasionally a right lower quadrant mass. Feeding intolerance is one of the early signs of NEC and with timely identification the disease can be treated conservatively with bowel rest and antibiotics. If untreated, NEC progresses rapidly to more advanced stages that require surgical intervention (11). As mentioned above, early feeding seems to be beneficial for extremely preterm and VLBW infants and is not associated with increased risk for NEC (4). Besides, there is good evidence that feeding with human breast milk has a protective effect against NEC, whereas formula increases the risk of this gastrointestinal condition (10). Meconium is not sterile and higher detection rates of potentially pathogenic bacteria in faeces of NEC infants suggest that a range of potentially pathogenic bacteria may collectively contribute to NEC pathogenesis (12). Considering also that serial rectal irrigation performed before surgery in children with Hirschsprung disease prevents enterocolitis (13), one could hypothesize that early meconium evacuation in extremely preterm born infants, which have immature intestinal motility, could prevent NEC, by counteracting both mechanical obstruction and overgrowth of potentially harmful pathogens, and by facilitating the flow of gastrointestinal content.

Delayed passage of meconium is identified as one of the risk factors for feeding intolerance in preterm VLBW neonates (1,14,15). The use of medications such as prokinetics (e.g. erythromycin, cisapride) to improve gut motility has failed to show significant benefits in VLBW neonates and is associated with adverse events (1). Nevertheless, several studies have evaluated the effect of induced meconium evacuation on TFF and feeding intolerance in neonates, with controversial results (1,16–25). In an observational study in 2007, Shim et al. reported that routine use of glycerine enema in infants resulted in full enteral feeds earlier than in the control group (median 16.0 vs 22.9 days; P

value <0.001) with a hazard ratio of 2.9 (95% confidence interval 1.8 to 4.8). This difference was greater for infants with birth weight (BW) < 1000 g (median 17.3 vs 28.1 days; P value < 0.001). Investigators also reported that the rate of sepsis was lower for VLBW infants in the glycerine enema group than for those in the control group (7.7% vs 27.8%; P value = 0.02). Thereafter, several RCTs have been conducted to further examine these findings (16,18–23), and have been subsequently summarized in systematic reviews and meta-analyses (1,24–27).

Ibrahim et al. conducted an open-label, pilot, randomized controlled trial (RCT) including infants with BW  $\leq$ 1,500 g comparing early aggressive meconium evacuation with twice-daily normal saline rectal washout to conventional management with glycerine suppositories, until full enteral feeds were reached. The study resulted in shorter TFF in children with birth weight 750-999 g receiving rectal washout as compared to those receiving glycerine suppositories, but no difference was noted in children with birth weight 1000-1500 g (16). However, an open-label RCT study with regular administration of glycerine suppositories to babies born at gestational age (GA) between 24 and 32 weeks for 10 days did not significantly reduce the TFF. There was no impact on secondary outcomes including sepsis, NEC, feed tolerance, duration of oxygen requirement, growth or age at discharge. Passage of first meconium was earlier in intervention group babies than controls, but the clinical significance was unclear (19). Similarly, a controlled multicentre RCT by Mena et al. that evaluated the use of normal saline enemas with glycerol versus simulation in infants with BW 500 - 1250 g did not find significant differences regarding the TFF and secondary outcomes including the number of episodes of late sepsis, hyperbilirubinemia, NEC, and intraventricular haemorrhage (IVH) (21). Two other RCTs, one that evaluated small volume saline enemas versus no intervention in infants with BW  $\leq$ 1500 g and GA  $\leq$ 32 weeks to accelerate meconium evacuation in VLBW infants (20), and another that compared the efficacy of glycerine suppository versus no intervention in preterm VLBW (BW 1000 - 1500 g) and preterm (GA 28 - 32 weeks) neonates to improve feeding tolerance (18), found no evidence of efficacy. Moreover, rectal stimulation and/or small volume saline enemas did not accelerate the normalization of stooling pattern in infants with a gestational age  $\leq$ 28 weeks (22). Finally, another RCT found that the administration of both glycerine enema and oral probiotics

(Golden diplococci) can significantly improve feeding tolerance and shorten the TFF (23).

Nevertheless, the last two studies were subject to the limitation of combining two different interventions in the same group, thus making it difficult to distinguish their effect (22).

A Cochrane meta-analysis by Anabrees et al. showed that prophylactic administration of glycerine laxatives did not reduce the TFF and did not influence secondary outcomes, including duration of hospital stay, mortality, patent ductus arteriosus (PDA), IVH, NEC, retinopathy of prematurity (ROP), bronchopulmonary dysplasia (BPD) and weight at hospital discharge. Prophylactic administration of glycerine laxatives resulted in improved stool passage over the first 48 hours of life (24). Similarly, another meta-analysis including the same RCTs concluded that the evidence for the use glycerine enemas or suppositories in premature infants is inconclusive (25). Less strict inclusion criteria were applied in a meta-analysis conducted by Deshmukh et al, suggesting that the use of glycerine suppositories, small-volume enema with glycerine or normal saline, or the administration of an oral osmotic agent, such as gastrografin, to evacuate the meconium did not reduce the TFF in preterm VLBW neonates. The authors proposed that the reason for this might be that these interventions do not influence the right colon or the small bowel. Additional limitations included the small sample size, inherent bias due to a lack of blinding of the intervention in some studies, and lack of a standard definition for full enteral feeding (1). Of note, other investigators conducted a systematic review of the available studies, choosing not to proceed to meta-analysis, pointing out that only two studies examined the same primary outcome. Furthermore, the authors underlined that all the interventions were carried out in a different way. The studies that examined the effect of enemas displayed slight differences regarding the use of enema volumes, the administration of enemas and the time between these administrations. Besides, the included studies were carried out all over the world, in different hospitals and all the hospitals had different policies on enteral feeding, use of TPN and infusion, which might have influenced the outcome of the studies and made it hard to draw an unambiguous conclusion (26).

The study by Haiden et al. is the one with the lowest GA and BW studied so far, namely 24 weeks and 491g, respectively (20). In none of the available studies the infants were fed exclusively with

breast milk. Furthermore, no study started enteral feeding soon after birth (within the first two hours of life) (1). To our knowledge, there are two ongoing RCTs evaluating TFF with induction of meconium evacuation: one including infants with GA 24 – 32 weeks and BW 500 – 1,500 g, comparing glycerine suppository vs sham suppository (registry number NCT02153606) and another including infants with BW <1,250 g, comparing glycerine suppository vs no intervention (registry number NCT01799629). One more study intending to compare three groups (glycerine suppository, rectal stimulation, and sham placebo) among preterm infants with BW ≤ 1500 g was also identified (registry number NCT02149407), but its recruitment status is unknown (28).

The Neonatal Intensive Care Unit (NICU) of University Children's Hospital in Uppsala is a tertiary unit caring for extremely preterm infants born as early as GA 22+0. The incidence of NEC, IVH, and PDA in infants born in GA 22+0 and 26+6 is approximately 15%, 20%, and 60%, respectively, and almost all infants are diagnosed with various degrees of BPD and ROP. All extremely preterm infants are fed exclusively with breast milk (mother's and/or donated), the first feeding given within one to two hours from birth. We strive to reach full enteral feeding within about 7 and 10 days in infants born in GA ≤ 26 weeks and 5 days in infants born GA 26-28 weeks, respectively.

## Study hypothesis

Regular intestinal lavage in preterm infants of GA between 22+0 and 26+6 weeks facilitates faeces evacuation, shortens the TFF and time to regaining of birth weight, thereby decreasing the risk of sepsis (through shorter intravascular access) and NEC.

## Study design

### **Interventional study design**

The study will be designed and conducted as a two-arm parallel, open-label, randomized controlled trial (RCT) at a tertiary-care hospital.

## **Masking**

No masking will be applied, in order not to expose the control group to sham interventions of no benefit or potential harm.

## **Allocation**

A blinded research coordinator will randomly assign eligible infants using a computer software-based randomization system (default) or sealed, numbered, and opaque envelopes (back-up), with a 1:1 allocation ratio, as soon as possible and not later than 24 hours from birth.

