## **Sample size calculation and estimated duration of the study**

Sample size calculation is based on the incidence of NEC, as the rarest of the events that will be studied, which is currently about 15% among extremely preterm infants at our unit, as mentioned above. For study power of at least 70%, confidence level of 5%, and an expected decrease of NEC incidence from 15% to 8%, each study arm should include about 100 participants (29). Each year, our unit treats about 70 infants born in GA 22+0 – 26+6. Supposing a participation rate of 70%, it is estimated that the recruitment period should last between 3 and 4 years, preliminarily starting during 2018. However, a recruitment period of maximum 5 years will be allowed.

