## **Feeding regimen and feeding intolerance guidelines (common for both groups)**

### Feeding regimen:

All infants born between GA 22+0 and 26+6 are fed exclusively with breast milk (mother's and/or donated), the first feeding given as soon as possible after birth (usually within one to two hours) and then 2-hourly. At day 1, the following scheme is applied:

- GA 26 – 28 v: total volume 80-90 ml/kg/day; enteral nutrition 2ml/kg every two hours, and the remaining is administered as PN through a central venous access.
- GA <26 v: total volume 90-100 ml/kg/day; enteral nutrition 1ml/kg every two hours, and the remaining is administered as PN through a central venous access.

The total feeding volume is advanced progressively on an individual basis, usually by 10-20ml/kg/day, to a final volume between 150 and 200ml/kg/day, striving not to exceed a weight loss of 10%, and depending on feeding tolerance. Full enteral nutrition is pursued within 5 days for GA 26 – 28 weeks and within 7-10 days for GA ≤26 weeks. PN is discontinued when enteral feeding reaches about 150 - 200 ml/kg/day, considering the child's growth development. Protein fortification is usually initiated when enteral nutrition constitutes more than 75-100 ml/kg/d (~50%) of total fluid volume.

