### **Refuse to enrollment and subject dropouts**

Refusals to enroll the study and dropouts of the study and the respective reasons will be documented and reported in the results. Effort will be made to replace each of these subjects with another infant of the same gestational age.

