### **Statistical analysis**

Numerical data with a gaussian distribution will be expressed as means (standard deviation), otherwise as medians (ranges). We will use the Anderson-Darling test to assess the normality of the data. Numerical values will be compared between intervention and control groups using t-tests or the Mann-Whitney U test. Categorical variables will be compared using  $\chi^2$  or Fisher's exact tests. Times to achieve full enteral feeding will be compared by the log rank test. Multiple Cox regression analysis will be used to adjust for covariates, such as gestational age and birth weight. IBM SPSS software (current version at the time of publication) will be used for all calculations and a p-value of <0,05 will be considered significant.

Interim analysis will be conducted when 35 infants have been recruited in each study arm (estimated about 1,5 years from study start). Another interim analysis will be conducted when 65 infants have been recruited in each study arm (estimated about 3 years from study start). Unplanned interim analysis will also be conducted in case of subjectively estimated too obvious difference between the groups regarding the primary outcomes, at any time during the study. The study will be discontinued as soon as an interim analysis shows statistically significant results regarding the primary outcomes or severe adverse events.

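### The plan specifies no stratification or blocking by gestational age, although gestational age sets the feeding scheme and the NEC comparison has no stated adjustment for it

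*Combined protocol and SAP*

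**What the plan says.** The Allocation section is the whole randomisation plan. A blinded coordinator assigns infants by computer, with opaque envelopes as reserve, "with a 1:1 allocation ratio, as soon as possible and not later than 24 hours from birth". No stratification factor, block scheme or minimisation is given there or elsewhere. The Masking section adds "No masking will be applied".

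The Feeding regimen section ties feeding to GA. Below 26 weeks the day-1 scheme is "enteral nutrition 1ml/kg every two hours, and the remaining is administered as PN through a central venous access"; at 26-28 weeks the two-hourly amount is 2 ml/kg. Full feeds are sought within 5 days at 26-28 weeks and within 7-10 days at 26 weeks or less. TFF and NEC (Bell stage II or more) are both primary outcomes.

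Under Statistical analysis, TFF is compared by the log rank test. Cox regression is to adjust for covariates, with GA and birth weight as examples. Categorical variables are compared by chi-square or Fisher's exact test. "Interim analysis will be conducted when 35 infants have been recruited in each study arm", again at 65 per arm, and a significant primary result at any look ends the study. Completion is at 100 per arm, with a ceiling of 130 per arm.

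Of refusals and dropouts the plan says: "Effort will be made to replace each of these subjects with another infant of the same gestational age".

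**The concern.** GA is known at birth, so it can be used within the 24-hour randomisation window. The plan itself makes it prognostic for TFF through the feeding scheme, and names it first among its covariates. If allocation ignores GA, the arms can differ in GA by chance, most of all at the first look, where the trial may already stop. Planned Cox adjustment gives TFF some protection. NEC has none stated: its test is crude.

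GA-matched replacement does not fill this gap. An infant of the same GA restores balance between arms only if it also enters the arm that lost a subject, and that bypasses random allocation. A refusal was never randomised and has no arm to restore. Choosing replacements by GA also conflicts with the consecutive recruitment described under Eligibility criteria.

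A smaller matter is that both planned looks and completion are defined by a count in each arm, which unblocked allocation does not reach at a fixed total.

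**Working it through.** **Inputs from the documents.** 1:1 ratio; looks at 35 and 65 per arm; completion at 100 and ceiling of 130 per arm; NEC 15% versus 8%; 5% level; power at least 70%.

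**Inputs assumed.** Simple (coin-toss) allocation, because no scheme is stated. A GA subgroup making up 20-50% of infants, because no GA mix is given.

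**1. The plan's own figure.** The sample size section concludes that "each study arm should include about 100 participants". With p1 = 0.15, p2 = 0.08 and mean 0.115:

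n = [z_alpha × √(2 × 0.115 × 0.885) + z_power × √(0.15 × 0.85 + 0.08 × 0.92)]² / 0.07²

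- Two-sided: (1.960 × 0.4512 + 0.524 × 0.4484)² / 0.0049 = 256 per arm.
- One-sided, with 1.645 in place of 1.960: 195 per arm.

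The figure of 100 is not reproduced. Two-sided power at 100 per arm is 34%. That is a separate matter, and nothing below depends on it.

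**2. Chance imbalance in GA.** Let X and Y be the subgroup counts in two arms of n infants, each Binomial(n, p). A gap of 10 points or more means |X − Y| of at least 4, 7 and 10 for n = 35, 65 and 100. Exact probabilities:

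| Assumed share p | 35 per arm | 65 per arm | 100 per arm |
|---|---|---|---|
| 20% | 29% | 15% | 9% |
| 30% | 36% | 21% | 14% |
| 50% | 40% | 25% | 18% |

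At 35 per arm, a gap of 20 points or more has probability 5% at p = 20% and 12% at p = 50%. The standard deviation of the gap at p = 30% is √(2 × 0.3 × 0.7 / n) = 11.0, 8.0 and 6.5 points.

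**3. What a gap does to NEC (illustration).** Assume a 30% subgroup and NEC of 15% overall.

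- If NEC in the subgroup is 20%, elsewhere it is (0.15 − 0.3 × 0.20) / 0.7 = 12.9%. A 10-point gap shifts the NEC difference by 0.1 × 7.1 = 0.7 points.
- If it is 30%, elsewhere it is (0.15 − 0.3 × 0.30) / 0.7 = 8.6%. The shift is 0.1 × 21.4 = 2.1 points.

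The sampling standard error at 35 per arm is √(2 × 0.15 × 0.85 / 35) = 8.5 points.

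**4. Per-arm counts.** Coin-toss allocation was simulated until both arms reach the required number (40,000 runs):

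| Required per arm | Mean total | 95th percentile |
|---|---|---|
| 35 | 77 | 88 |
| 65 | 139 | 154 |
| 100 | 211 | 229 |

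The larger arm passes 130 before the smaller reaches 100 in about 4% of runs. Unequal arms cost almost no power: 35% at 90 versus 110, against 34% at 100 versus 100.

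**5. With blocks.** Taking blocks of 4 as an example, each stratum differs by at most 2 between arms. With two strata the total difference is at most 4, so 35, 65 and 100 in both arms are reached by totals of at most 74, 134 and 204.

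**The case against.** **Silence is not absence.** A reader might infer that the trial uses neither strata nor blocks. The documents do not say so; the software may apply either. What stands is that none is specified, so none is required and none can be verified. The imbalance figures are conditional on simple allocation.

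**GA is not ignored.** A reader might infer that GA is left unhandled. Cox adjustment is planned, and it covers TFF, the outcome that the feeding scheme affects directly. What remains is NEC, and the loose wording that offers GA only as an example covariate.

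**The purpose of replacement is not stated.** A reader might take GA-matched replacement as the plan's device for balancing the arms. The section does not say this, and keeping up the sample's size and GA mix is an equally natural purpose. The case for deleting it holds whatever the purpose was.

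**Chance imbalance is not bias.** The type I error of a test under simple randomisation already allows for it, and the illustrated shift of 0.7-2.1 points is small beside a standard error of 8.5. The larger danger at the first look is the stopping rule itself, which is a separate issue. This stands, and it limits the point to an improvement.

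**Per-arm counts matter little.** The ceiling of 130 per arm absorbs nearly all of the drift, and a look can wait for the smaller arm. This stands too.

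**Blocks have a price.** In an unmasked single-centre trial they make some assignments easier to guess. Varying, concealed block sizes reduce this but do not remove it.

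**Conclusion.** The point holds as a worthwhile, low-cost design improvement. The plan specifies no stratification, blocking or minimisation, although GA affects one primary outcome by design and the other has no stated adjustment for it. If allocation is simple and a GA subgroup makes up 20-50% of infants, a gap of 10 points or more between arms arises in 29-40% of trials at 35 per arm, falling to 9-18% at 100. The gain from stratifying is GA balance, mainly for NEC and at the early look. The drift in arm counts is minor.

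The documents do not support saying that the randomisation is invalid, or that the trial is known to be unstratified. The exact percentages rest on the assumed GA mix; that sizeable imbalance is common at 35 per arm holds across the whole assumed range.

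**What to change.** 1. In the Allocation section, specify permuted blocks of randomly varying, undisclosed size within a few GA strata, for both the software and the reserve envelopes. Keep block sizes from anyone who enrols or treats infants.
2. Before setting the strata, reconcile the Feeding regimen section. Its day-1 scheme places infants of 26 weeks with 26-28 only (the other group is <26), while its full-feed target names them in both groups (≤26 and 26-28).
3. In the Statistical analysis section, account for the strata in both primary analyses: a stratified log rank test or Cox model for TFF, and a stratified or adjusted comparison for NEC. Stratifying the allocation without this leaves the NEC test crude.
4. Delete the GA-matched replacement of refusals and dropouts, and continue to document and report both.

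The cost is one software setting, one set of envelopes per stratum and a few sentences of protocol text. The target number of infants does not change. The downside is slightly greater predictability of assignment, limited by the varying and concealed block sizes.
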